3.3 OPERATIONAL AND CONCEPTUAL DESCRIPTION OF THE VARIABLES

3.3.1 Simple support and double support time

Simple support is characterized by contact with the ground with only one foot. When the two feet are in contact with the ground, the double support is characterized. (VILLARDI et al, 2005). Variables will be expressed in seconds.

3.3.2 Stride and step length

Step is the range of gait between the initial contact of one foot and the initial contact of the other foot. Past is based on the actions of a member, it lasts the interval between two

sequential contacts of the same member in the ground (PERRY, 2005). Both will be expressed in centimeters.

3.3.3 Adductor moment in gait

The external adductor moment is the biomechanical measurement for medial load of the knee, the larger the external adductor moment the greater the load in the medial compartment of the knee. Thus, this shows a large incidence in OA, being a better predictor of OA progression. The frontal evaluation of the knee can elucidate the effect of the prosthesis on the response of the medial load in the knee and eventual compensations in the contralateral knee that can contribute to the progression of OA. (ALNAHDI et al, 2011). The variable will be expressed in N/m.

3.3.4 Knee flexion angle in gait

The knee flexion joint angle is measured between the longitudinal axis of the thigh and the longitudinal axis of the leg, knowing that in the anatomical reference position all articular angles are equal to zero (HALL, 2013). The knee flexion in the load response will be measured using the Vicon MX system. The variable will be expressed in degrees.

3.3.5 Electromyographic activity

The electromyographic signal is expressed in root mean square (RMS), obtained through the mean and median frequency of the signal and temporal analysis of the signal. The RMS indicates the chronological activation of the motor units and the amplitude of the muscular activation before the applied exercise (GONÇALVES e SILVA, 2007).

The variable will be expressed as a percentage by normalizing the maximum voluntary contraction. It will be evaluated by the Telemyo DTS electromyograph (NoraxonTM).

3.3.6 Self-reported functionality by WOMAC (*Western Ontario and McMaster Universities Osteoarthritis Index*)

The WOMAC questionnaire has 24 items distributed in the dimensions pain, stiffness and function with scores from 0 to 100, being 0 = none, 25 = few, 50 = moderate, 75 = intense and 100 = very intense. The higher the final score, the greater the functional impairment of the individual (GIESINGER et al, 2015). In this study the validated version for the Portuguese language will be used (Fernandes et al, 2003).

3.3.7 Kinesiophobia

Excessive, irrational and debilitating fear of movement and physical activity that results in feelings of vulnerability to pain or fear of injury recurrence is classified as kinesiophobia and can be assessed by the Tampa Scale of Kinesiophobia (SIQUEIRA et al, 2007). This variable is dimensionless and will be evaluated by the TAMPA scale.

3.3.8. Functional mobility by TUG (*Timed Up And Go*)

The TUG assesses the functional capacity of individuals by means of temporal analysis to perform lifting, walking, turning and sitting (PODSIADLO e RICHARDS, 1991). It is a temporal variable that will be measured in seconds.

3.3.9 Center of gravity oscillation speed

Center of gravity is the point at which the torques produced by the weights of the body segments are equal to zero, this measure oscillates in the direction of the largest mass of a moving body (HALL, 2013). This variable is measured in seconds and will be evaluated through the VSR Equilibrium Platform.

3.3.10 Displacement and velocity of pressure center

Pressure center (COP) is the point and application of ground reaction force in response to forces generated by a body in contact with the surface. The COP indicates the trajectory displacement of the soil reaction force vector (HAMILL e KNUTZEN, 2012). The parameters of the COP will be obtained from the displacement and velocity of the center of gravity by routine elaborated in MATLAB. The displacement of the COP will be expressed in centimeters and the speed of oscillation in centimeters per second.

3.4 INSTRUMENTS

3.4.1 Vicon MX System

The Vicon MX system is a passive system that measures reflected light through markers placed on the surface of the human body. This integrated system is indicated for the analysis and measurement of human movement, among them the clinical evaluation of gait (VICON MX, 2006).

For the acquisition of the kinematics data of the gait will be used the system Vicon Bonita 10 MX Giganet (Oxford Metrics Group; UK) Consisting of 10 beautiful cameras with LED emitting component (Light Emitting Diode) that surrounds the lens of each camera, maximum frequency of 250 frames per second (fps), 720p and 4-12mm lenses, 11 cables for Connect the beautiful cameras to giganet unit.

All cameras are connected to the Giganet unit, which feeds the cameras and serves as an instrument for synchronization and integration with other biomechanical laboratory instruments (force platform and electromyography). Once in the video memory, the data is transferred to the computer named Nexus® that will perform the processing and reconstruction of the three-dimensional image of the markers by means of a biomechanical model and mathematical algorithms.

3.4.2 AMTI OR6-7 Force Platform

For the study, two AMTI OR6-7 Force Platforms will be used, placed side by side in the center of the course where the individual will gait. Each power platform consists of two rigid surfaces (top and bottom) interconnected by load cell force sensors. This type of platform is a device that has its electrical resistance varied as a function of the mechanical deformation of the same (BARELA e DUARTE, 2011).

The AMTI OR6-7 Force Platform uses four precision-mounted tension gauges to measure forces at any given moment. The measurement of the orthogonal force occurs along

the X, Y, Z axes and the momentum on these axes, producing a total of six outputs. It has vertical capacity to evaluate 4500, 8900 or 17800 Newtons (AMTI, 2010).

Data sampling will occur at 100Hz. The extended signal will be synchronized with the Vicon gait analysis system.

3.4.3 Noraxon Electromyograph

The electromyographic activation of the lower limb muscles will be measured using the Noraxon MyoMuscle v. 3.8. The standard system has EMG preamplifiers, but can be synchronized with other biomechanical sensors. In addition it can operate with up to 16 channels in wireless system, making it easier to capture the signal during the movement. The double electrodes are self-adhesive and attached to the sensor, which is attached to the skin with double-sided tape. The data collected by the electrode is transmitted immediately to the receiver (NORAXON, 2015). The electromyographic data collection will be synchronized to the gait collection performed with the Vicon MX System.

3.4.4 Timed up and Go Test (TUG)

The TUG was developed to evaluate the functional mobility of the elderly. The classification of the elderly is performed according to the time required to complete the task as follows: up to 10 seconds is the time considered normal for healthy, independent adults without risk of falls; Between 11-20 seconds is expected for frail or disabled elderly, with partial independence and with low risk of falls; Above 20 seconds indicates significant deficit of physical mobility and risk of falls (PODSIADLO e RICHARDS, 1991).

This instrument shows excellent intra-observer and inter-observer reliability (ICC = 0.99). The concurrent validity was evaluated by comparing it with the Berb Balance Scale (r = -0.81), walking speed (Pearson r = -0.61) and the Barthel Index (r = -0.51), presenting a Moderate to good correlation between the tests. (PODSIADLO e RICHARDS, 1991). High TUG times were significant in predicting the occurrence of falls and decline in ADLs, identifying individuals with impaired functional capacity (LIN e WOLLACOTT, 2005).

3.4.5 Neurocom Balance Platform

The data will be collected using the SMART EquiTest CRS platform and the NeuroCom Balance Manager software (NeuroCom International, Inc., Clakamas, OR), which is a computerized tool for assessing and managing balance and mobility disorders.

The SMART EquiTest CRS platform consists of dual force platform, visual environment, upper bar with support for the patient harness, LCD monitor for the participant and a computer for system operation.

NeuroCom Balance Manager software measures postural control based on oscillation speed, recorded in degrees / second. The calculation used to determine the oscillation speed in the SET protocol is not publicly available. According to the interpretation suggested by NeuroCom, higher score represents a potential deficit in the balance (NEUROCON, 2010).

3.4.6 Womac Scale (Western Ontario and McMaster Universities Osteoarthritis Index)

The Womac score (ANNEX A) for osteoarthrosis is a valid and reliable instrument, specific for knee OA. Evaluates pain, stiffness and physical functions. This questionnaire consists of three domains - pain, stiffness and function - and must be answered in relation to the intensity of pain, joint stiffness and level of functionality perceived by the individual in the last 72 hours. The questions are presented in Likert scale, where each one has a score ranging from 0 to 100, thus distributed: 0 = none; 25 = few; 50 = moderate; 75 = intense; 100 = very intense. The final score will be obtained by summing the values of all the subjects in each question, the average is obtained, and the values are presented for each section or domain (IVANOVITH, 2002).

3.4.7 Tampa Scale of Kinesiophobia

Kinesiophobia is defined as excessive, irrational and debilitating fear of movement and physical activity, with consequent feeling of vulnerability to pain or fear of relapse of the problem. The cover scale for kinesiophobia (APPENDIX B) will be used to quantify fear of movement. The validated Brazilian version of the scale will be used. (SIQUEIRA et al, 2007). Each instruction is scored on a 4-point Likert scale with scores ranging from 1 "totally disagree"

to 4 "strongly agree". It presents as possible results the maximum score of 68 points and the minimum score of 17 points. The higher the score, the higher the kinesiophobia.

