ATTACHMENT B - TAMPA SCALE OF KINESIOPHOBIA

Here are some things other patients told us about their pain. For each statement, please, provide a score from 1 to 4 in case you agree or disagree with the statement. First, you must think if you agree or disagree and then say you agree/disagree entirely or partially.

		Entirely disagree	Partially disagree	Partially agree	Entirely agree
1.	I'm afraid of getting hurt if I exercise.	1	2	3	4
2.	If I tried to overcome this fear, my pain would increase.	1	2	3	4
3.	My body is telling me there is something very wrong happening with me.	1	2	3	4
4.	My pain would probably be relieved if I made some exercises.	1	2	3	4
5.	People are not taking my medical condition seriously.	1	2	3	4
6.	The injury put my body at risk for the rest of my life.	1	2	3	4
7.	Pain always means that my body is hurt.	1	2	3	4
8.	Just because something worsens my pain, it doesn't mean it is dangerous.	1	2	3	4
9.	I'm afraid of getting hurt by accident.	1	2	3	4
10.	The safest attitude I can take in order to prevent my pain from getting worse is just to be careful to not to make any unnecessary movement.	1	2	3	4
11.	I wouldn't fell so much pain if something really dangerous was not happening with my body.	1	2	3	4
12.	Although I feel pain, I would be better if I was physically active.	1	2	3	4
13.	Pain warns me when to stop exercising in order to not getting hurt.	1	2	3	4
14.	It is not really safe for a person with problems similar to mine to be physically active.	1	2	3	4
15	I cannot do all the things normal people do, because I easily get hurt.	1	2	3	4
16.	Although something causes me a lot of pain, I don't think it is really dangerous.	1	2	3	4
17.	Nobody should make exercises when in pain.	1	2	3	4

Table 1 - Tampa Scale for Kinesiophobia - Brazil.

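### The protocol scores all 17 Tampa items from 1 to 4 towards agreement and states no reversal for items 4, 8, 12 and 16, where agreement means less fear

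*Protocol*

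**What the plan says.** Protocol section 3.4.7 says of the scale that "Each instruction is scored on a 4-point Likert scale with scores ranging from 1", the label for complete disagreement, up to 4, the label for complete agreement. It gives 17 and 68 as the lowest and highest possible totals and adds: "The higher the score, the higher the kinesiophobia". On the source of the instrument it says only: "The validated Brazilian version of the scale will be used", with a citation.

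Attachment B prints the 17 statements, each with the same columns 1 to 4 running from disagreement to agreement. The patient's instruction is: "For each statement, please, provide a score from 1 to 4 in case you agree or disagree with the statement". The caption is "Table 1 - Tampa Scale for Kinesiophobia - Brazil". Among the statements are item 4 ("My pain would probably be relieved if I made some exercises"), item 8 ("Just because something worsens my pain, it doesn't mean it is dangerous"), item 12 ("Although I feel pain, I would be better if I was physically active") and item 16, which says that something very painful need not be truly dangerous.

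No scoring key accompanies the attachment. Sections 3.3.7 and 3.5.2 and the data-processing text that follows section 3.5.5 do not mention recoding, and neither does the SAP. The SAP lists the scale for mean and standard deviation and leaves it out of the variables for the 3x2 analysis of variance.

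**The concern.** The per-item rule and the stated direction of the total cannot both hold for items 4, 8, 12 and 16. A patient who believes that exercise would help, or that pain does not signal danger, is less afraid of movement, but under the written rule each such answer adds points to the fear score. The other 13 items run the stated way, so the total still rises with fear overall, but four items pull against it.

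The abstract and section 1.1 name kinesiophobia as an aim, and section 3.8 includes it in the hoped-for benefit. Section 1.1 also cites evidence that pain education can change the belief that pain means damage. Items 8 and 16 ask about that link between pain and danger, so some of the items affected are ones the intervention might plausibly move.

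**Working it through.** **Inputs.** From section 3.4.7: item scores 1 to 4, total 17 to 68, higher means more fear. From Attachment B: 17 items, of which four (4, 8, 12, 16) are worded so that agreement means less fear, leaving 13 worded towards fear.

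**The plan's own range.** 17 × 1 = 17 and 17 × 4 = 68. These are the arithmetic limits with or without reversal, so the stated range is not itself an error. The question is which patients land at its ends.

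**Totals for clear-cut answer patterns.**

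| Pattern | As written | With reversal (5 minus response) |
|---|---|---|
| Most fearful, consistent | 13×4 + 4×1 = 56 | 17×4 = 68 |
| Least fearful, consistent | 13×1 + 4×4 = 29 | 17×1 = 17 |
| Agrees fully with everything | 17×4 = 68 | 13×4 + 4×1 = 56 |
| Disagrees fully with everything | 17×1 = 17 | 13×1 + 4×4 = 29 |

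As written, the span from least to most fearful is 56 − 29 = 27 points, against 68 − 17 = 51 with reversal; 27/51 = 53%. With reversal, the ends of the stated range coincide with least and most fearful.

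**Error for one patient.** Let F be the sum of the 13 fear-worded items and S the raw sum of the other four (4 to 16). The as-written total is F + S and the reversed total is F + (20 − S), so the difference is 2S − 20. It is −12 at S = 4, zero at S = 10 and +12 at S = 16.

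**Order of two patients.** Their as-written difference is ΔF + ΔS and their reversed difference is ΔF − ΔS. These have opposite signs exactly when |ΔS| > |ΔF|. Example: two patients both answer 2 on all 13 fear-worded items, so F = 26. One answers 3 on the four low-fear items and the other answers 2.
- As written: 26 + 12 = 38 and 26 + 8 = 34.
- With reversal: 26 + 8 = 34 and 26 + 12 = 38.

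The less fearful patient gets the higher fear score.

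**Raw difference between arms.** Assume each of the four items shifts k times as far towards less fear as each of the other 13. The as-written difference is then (13 − 4k)/(13 + 4k) of the correct one.

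| k | Share of the raw difference kept |
|---|---|
| 0 | 100% |
| 0.5 | 11/15 = 73% |
| 1 | 9/17 = 53% |
| 1.5 | 7/19 = 37% |
| 3.25 | 0, with the sign changing beyond |

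For instance, if every item moves 0.25 points towards less fear (k = 1), the reversed total falls by 17 × 0.25 = 4.25 points and the as-written total by 9 × 0.25 = 2.25.

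**Standardised difference.** The standard deviation changes too, so this can go either way. A simulation assumed one common factor, equal loadings of 0.4, 0.6 or 0.8, item cut points at −0.75, 0 and 0.75, a shift of 0.5 SD on the factor and 200,000 patients per arm. The ratio of as-written to correct standardised difference, across the three loadings, was:

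| k | Ratio |
|---|---|
| 0 | 1.45 to 1.80 |
| 0.5 | 1.07 to 1.33 |
| 1 | 0.77 to 0.95 |
| 1.5 | 0.54 to 0.67 |

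The documents give neither k nor loadings, so these figures show a range and not an expected loss.

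**The case against.** The strongest reply is that adopting a validated instrument by citation normally brings its scoring with it. Section 3.4.7 describes the response options, the range and the direction; it never says in so many words that raw answers are summed without recoding. The stated range and direction fit correct scoring well. On this reading the gap is a key that was not reprinted, and nothing shows that the team would ignore it. This stands as a limit on the finding: the documents cannot show that any score will be wrong. It does not remove the conflict, because the only item rule in the documents covers every item alike, and an analyst working from them would sum the raw responses.

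The likely effect can also be called small or undetermined. The 12-point error needs the same extreme answer on all four items; with S between 8 and 12 the error is at most 4 points. Under some assumptions the standardised difference rises, and nothing in the documents supports a k as large as 3.25. The leaflet in Appendix A is mostly practical advice, and both arms receive verbal guidance, so a particular shift on items 8 and 16 is conjecture. A common scoring rule also cannot create a difference between arms whose responses do not differ. All of this is fair, and it is why no single loss figure is claimed. The error in individual totals, and so potentially in the reported means and standard deviations, does not depend on those assumptions.

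**Conclusion.** The concern holds, as a statement about the rule as written. For four of the 17 items that rule runs against the direction the protocol assigns to the total, and no reversal is stated in either document. The exact consequences of following it are consistent extremes of 29 and 56 instead of 17 and 68, an individual error of 2S − 20, and reversed ordering of any two patients who differ more on the four items than on the 13. Any effect on the comparison of arms rests on assumed values of k and the loadings. Whether mis-scoring would occur depends on whether the team follows section 3.4.7 literally or applies a key from the cited version.

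The reach is limited. TUG is the primary outcome, and the SAP plans no test of kinesiophobia, so the significance level, power and sample size are untouched. The response form is not at fault, since it only records agreement. The point should be corrected because it concerns a named aim and the correction is nearly free.

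**What to change.** Check the scoring key of the cited Brazilian version. Then state in section 3.4.7 and in the SAP that items 4, 8, 12 and 16 are recoded as 5 minus the response before the 17 items are summed, at all three visits, and print the key beside Attachment B. The response form can stay as it is.

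The cost is one sentence in each document and one line of data processing. The form already records item responses, so nothing has to be collected again.

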3.5 DATA COLLECTION

The study will be developed in the dependencies of the Laboratory of Biomechanics of the Center for Health Sciences and Sports of UDESC. In the preoperative period the subjects will be informed about their physical conditions as well as signs and symptoms of the postoperative period. One group (GI) will receive this information verbally and one leaflet while the other group (GC) will receive only verbal information. The allocation in these groups will be through a lottery, carried out by a member of the team who will not participate in the evaluation stages.

This staff member will read the booklet individually for each GI participant, in a reserved room, before handing out the leaflet to take home. GI participants will be encouraged to reread the information in the home environment and will be asked about the completion of this in the following steps by the staff member responsible for the blinding.

All participants included in the study will perform the kinematic, kinetic and electromyographic gait analysis as well as evaluation of fear of movement, functional mobility and self-perceived functionality in the pre (baseline)-and postoperative period (6 weeks and after 6 months).

The total duration of each evaluation will be approximately 2 (two) hours and 30 (thirty) minutes and all collections will be carried out by the same team. The participant will be allowed to stop the test if they feel pain or become fatigued. The procedures for collecting the data will be performed in 5 steps, described below.

3.5.1 Stage 1 - Anthropometric measurements

Body mass and stature will be measured by means of a mechanical scale of up to 150 kg Filizola® brand, with a resolution of 0.1 kg, and by means of a portable Wiso stadiometer, with a resolution of 0.1 cm. The diameters and lengths required for insertion into the anthropometric model of kinematic analysis will be measured by a pachymeter and a tape measure, both with resolution of 0.1 cm.

3.5.2 Stage 2 - Self-referenced functionality and kinesiophobia

The Brazilian version of the kinesiophobia cover scale and the WOMAC scale will be applied before each gait evaluation in the three periods (pre, post 6 weeks and post 6 months).

3.5.3 Stage 3 – gait analysis

The subjects will be previously instructed to wear swimsuits in order to allow the placement of the markers in the anatomical points and the reading of the same ones by the cameras. All patients will be procedurally oriented and instructed on the tasks to be performed.

Before each collection, the calibration of the Vicon system will be performed. A Tshaped metal structure composed of two rods (containing a total of 5 14 mm reflective markers) will be used to determine the reference coordinates of the laboratory (X, Y and Z). The dynamic calibration will be performed, where the rod will be moved in all planes, generating location and orientation data of the cameras inside one. In static calibration the stem will be placed in the center of the collection area. Standard deviation errors less than 1 mm between known distances between markers.

Afterwards, thirty-two reflective spherical markers (14 mm in diameter) with double faces in specific anatomical points will be fixed in the subject, which will serve as reference for the motion analysis capture system. The markers will be placed in the manubrium, xiphoid process, seventh cervical vertebra, tenth thoracic vertebra, and bilaterally in the following points: acromion, anterior superior iliac spine, posterior superior iliac spine, major femoral tuberosity, lateral thigh region, condyle Lateral femoral, medial femoral condyle, fibular head, anterior tibial tuberosity, lateral malleolus, medial malleolus, first metatarsal head, fifth metatarsal head, and calcaneus.

Also, the electrodes and WiFi sensors of the Noraxon Electromyograph will be glued with double-sided tape on clean skin with cotton soaked in alcohol. The electrodes will be positioned on the long head of the femoral biceps, rectus femoris, vastus lateralis and vastus medialis following the position recommended by the SENIAM (2016).

You will be asked to walk on a 5-meter walkway, performing four trials. During the course of the gait, the participant must step on each of the lower limbs on one of the AMTI force platforms without being aware of this. After the collection, the data will be transported to the Visual 3D System, for measurement and analysis.

